7.2.3. Atezolizumab Special warnings and precautions for use

In order to improve the traceability of biological medicinal products, the trade name and the batch number of the administered product should be clearly recorded (or stated) in the patient file.

Most immune-mediated adverse reactions that occurs during treatment with atezolizumab are reversible with the interruptions of atezolizumab and initiation of corticosteroids and/or supportive care. Immune-mediated adverse reactions affecting more than one body system have been observed. Immune-mediated adverse reactions with atezolizumab may occur after the last dose of atezolizumab.

For suspected immune-mediated adverse reactions, thorough evaluation to confirm aetiology or exclude other causes should be performed. Based on the severity of the adverse reaction, atezolizumab should be withheld and corticosteroids administered. Upon improvement to Grade ≤ 1 , corticosteroid should be tapered over ≥ 1 month. Based on limited data from clinical studies in patients whose immune-mediated adverse reactions could not be controlled with systemic corticosteroid use, the administration of other systemic immunosuppressants may be considered.

Atezolizumab must be permanently discontinued for any Grade 3 immune-mediated adverse reaction that recurs and for any Grade 4 immune-mediated adverse reactions, except for endocrinopathies that are controlled with replacement hormones.

1) Pulmonary events

Cases of pulmonary events, including dyspnea, cough, fatigue, pulmonary infiltrates and pneumonitis, have been observed in clinical trials with atezolizumab. Patients should be monitored for pulmonary signs and symptoms.

2) Hepatic events

Immune-mediated hepatitis has been associated with the administration of atezolizumab. Patients eligible for study treatment must have adequate liver function, as manifested by measurements of total bilirubin and hepatic transaminases; liver function will be monitored throughout study treatment. Management guidelines for hepatic events are provided in Appendix 1.

3) Gastrointestinal events

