AST/ALT is within normal limits at baseline and increases to 3ULN to 10ULN or AST/ALT is ULN to 3ULN at baseline and increases to 5ULN to 10 ULN or AST/ALT is 3ULN to 5ULN at baseline and increases to 8ULN to 10ULN	
 Monitor LFTs more frequently until return to baseline values. Withhold atezolizumab for up to 12 weeks after event onset. ^a 
Events of 5 days' duration:
 
 Consider initiating treatment with corticosteroids equivalent to 1-2 mg/kg/day oral prednisone. If event resolves to baseline or to Grade 1 or better, resume atezolizumab. ^b If event does not resolve to baseline or to Grade 1 or better while withholding atezolizumab, permanently discontinue atezolizumab and contact Medical Monitor. ^c
AST or ALT increases to 10ULN or total bilirubin increases to 3ULN	
 Permanently discontinue atezolizumab and contact Medical Monitor. ^c Consider patient referral to gastrointestinal specialist for evaluation and liver biopsy to establish etiology of hepatic injury.

	
 • Initiate treatment with corticosteroids equivalent to 1-2 mg/kg/day oral prednisone. • If event does not improve within 48 hours after initiating corticosteroids, consider adding an immunosuppressive agent. • If event resolves to baseline, taper corticosteroids over ≥ 1 month.
--	---

LFT liver function test; ULN = upper limit of normal.

^a Atezolizumab may be withheld for a longer period of time (i.e., > 12 weeks after event onset) to allow for corticosteroids (if initiated) to be reduced to the equivalent of ≤ 10 mg/day oral prednisone. The acceptable length of the extended period of time must be based on assessment of benefit-risk by the investigator and in alignment with the protocol requirement for duration of treatment and documented by the investigator. Medical Monitor is available to advise as needed.

^b If corticosteroids have been initiated, they must be tapered over ≥ 1 month to the equivalent of ≤ 10 mg/day oral prednisone before atezolizumab can be resumed.

^c Resumption of atezolizumab may be considered in patients who are deriving benefit and have fully recovered from the immune-mediated event. The decision to rechallenge patients with atezolizumab should be based on investigator's assessment of benefit-risk and documented by the investigator (or an appropriate delegate). Medical Monitor is available to advise as needed.

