C) Management Guidelines for Gastrointestinal Events (Diarrhea or Colitis)

Event	Management
Diarrhea or colitis, Grade 1	
 Continue atezolizumab. Initiate symptomatic treatment. Endoscopy is recommended if symptoms persist for > 7 days. Monitor closely.
Diarrhea or colitis, Grade 2	
 Withhold atezolizumab for up to 12 weeks after event onset.^a Initiate symptomatic treatment. Patient referral to GI specialist is recommended. For recurrent events or events that persist > 5 days, initiate treatment with corticosteroids equivalent to 1-2 mg/kg/day oral prednisone. If event resolves to Grade 1 or better, resume atezolizumab.^b If event does not resolve to Grade 1 or better while withholding atezolizumab, permanently discontinue atezolizumab and contact Medical Monitor.^c
Diarrhea or colitis, Grade 3	
 Withhold atezolizumab for up to 12 weeks after event onset.^a Refer patient to GI specialist for evaluation and confirmatory biopsy. Initiate treatment with corticosteroids equivalent to 1-2 mg/kg/day IV methylprednisolone and convert to 1-2 mg/kg/day oral prednisone or equivalent upon improvement. If event resolves to Grade 1 or better, resume atezolizumab.^b If event does not resolve to Grade 1 or better while withholding atezolizumab, permanently discontinue atezolizumab and contact Medical Monitor.^c
Diarrhea or colitis, Grade 4	
 Permanently discontinue atezolizumab and contact Medical Monitor.^c Refer patient to GI specialist for evaluation and confirmatory biopsy. Initiate treatment with corticosteroids equivalent to 1-2 mg/kg/day IV methylprednisolone and convert to 1-2 mg/kg/day oral prednisone or equivalent upon improvement. If event does not improve within 48 hours after initiating corticosteroids, consider adding an immunosuppressive agent. If event resolves to Grade 1 or better, taper corticosteroids over 1 month.

^a Atezolizumab may be withheld for a longer period of time (i.e., > 12 weeks after event onset) to allow for corticosteroids (if initiated) to be reduced to the equivalent of ≤ 10 mg/day oral prednisone. The acceptable length of the extended period of time must be based on assessment of benefit-risk by the investigator and in alignment with the protocol requirement for duration of treatment and documented by the investigator. Medical Monitor is available to advise as needed.

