^a Atezolizumab may be withheld for a longer period of time (i.e., >12 weeks after event onset) to allow for corticosteroids (if initiated) to be reduced to the equivalent of \leq 10 mg/day oral prednisone. The acceptable length of the extended period of time must be based on assessment of benefit-risk by the investigator and in alignment with the protocol requirement for duration of treatment and documented by the investigator. Medical Monitor is available to advise as needed.

^b If corticosteroids have been initiated, they must be tapered over \geq 1 month to the equivalent of \leq 10 mg/day oral prednisone before atezolizumab can be resumed.

^c Resumption of atezolizumab may be considered in patients who are deriving benefit and have fully recovered from the immune-mediated event. The decision to rechallenge patients with atezolizumab should be based on investigator's assessment of benefit-risk and documented by the investigator (or an appropriate delegate). Medical Monitor is available to advise as needed.

E) Management Guidelines for Ocular Events

Event	Management
Ocular event, Grade 1	
 Continue atezolizumab. Patient referral to ophthalmologist is strongly recommended. Initiate treatment with topical corticosteroid eye drops and topical immunosuppressive therapy. If symptoms persist, treat as a Grade 2 event.
Ocular event, Grade 2	
 Withhold atezolizumab for up to 12 weeks after event onset.^a Patient referral to ophthalmologist is strongly recommended. Initiate treatment with topical corticosteroid eye drops and topical immunosuppressive therapy. If event resolves to Grade 1 or better, resume atezolizumab.^b If event does not resolve to Grade 1 or better while withholding atezolizumab, permanently discontinue atezolizumab and contact Medical Monitor.^c
Ocular event, Grade 3 or 4	
 Permanently discontinue atezolizumab and contact Medical Monitor.^c Refer patient to ophthalmologist. Initiate treatment with corticosteroids equivalent to 1-2 mg/kg/day oral prednisone. If event resolves to Grade 1 or better, taper corticosteroids over 1 month.

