^a Atezolizumab may be withheld for a longer period of time (i.e., >12 weeks after event onset) to allow for corticosteroids (if initiated) to be reduced to the equivalent of ≤ 10 mg/day oral prednisone. The acceptable length of the extended period of time must be based on assessment of benefit-risk by the investigator and in alignment with the protocol requirement for duration of treatment and documented by the investigator. Medical Monitor is available to advise as needed.

^b If corticosteroids have been initiated, they must be tapered over ≥ 1 month to the equivalent of ≤ 10 mg/day oral prednisone before atezolizumab can be resumed.

^c Resumption of atezolizumab may be considered in patients who are deriving benefit and have fully recovered from the immune-mediated event. The decision to rechallenge patients with atezolizumab should be based on investigator's assessment of benefit-risk and documented by the investigator (or an appropriate delegate). Medical Monitor is available to advise as needed.

F) Management Guidelines for Immune-Mediated Myocarditis

Event	Management
Immune-mediated myocarditis, Grade 2-4	
• Permanently discontinue atezolizumab and contact Medical Monitor.^a• Refer patient to cardiologist.• Initiate treatment as per institutional guidelines and consider antiarrhythmic drugs, temporary pacemaker, ECMO, or VAD as appropriate.• Initiate treatment with corticosteroids equivalent to 1-2 mg/kg/day IV methylprednisolone and convert to 1-2 mg/kg/day oral prednisone or equivalent upon improvement.• If event does not improve within 48 hours after initiating corticosteroids, consider adding an immunosuppressive agent.• If event resolves to Grade 1 or better, taper corticosteroids over \geq 1 month.

^a Resumption of atezolizumab may be considered in patients who are deriving benefit and have fully recovered from the immune-mediated event. Patients can be re-challenged with atezolizumab only after approval has been documented by both the investigator (or an appropriate delegate) and the Medical Monitor.

G) Management Guidelines for Infusion-Related Reactions and Cytokine-Release Syndrome

Event	Management

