
vasopressin) and/or hypoxia requiring high-flow oxygen ^d by nasal cannula, face mask, non-rebreather mask, or venturi mask
	
monitoring in the ICU is recommended. Administer IV fluids as clinically indicated, and manage constitutional symptoms and organ toxicities as per institutional practice.
 
 Rule out other inflammatory conditions that can mimic CRS (e.g., sepsis). If no improvement within 24 hours, initiate workup and assess for signs and symptoms of HLH or MAS. Administer IV corticosteroids (e.g., methylprednisolone 2 mg/kg/day or dexamethasone 10 mg every 6 hours). Consider anti-cytokine therapy.^e Hospitalize patient until complete resolution of symptoms. If no improvement within 24 hours, manage as per Grade 4, that is, admit patient to ICU and initiate hemodynamic monitoring, mechanical ventilation, and/or IV fluids and vasopressors as needed; for patients who are refractory to anti-cytokine therapy, experimental treatments may be considered at the discretion of the investigator and in consultation with the Medical Monitor.

Grade 4 ^a fever ^b with hypotension requiring multiple vasopressors (excluding vasopressin) and/or hypoxia requiring oxygen by positive pressure (e.g., CPAP, BiPAP, intubation and mechanical ventilation)
	
 Permanently discontinue atezolizumab and contact Medical Monitor.^e Administer symptomatic treatment.^c Admit patient to ICU and initiate hemodynamic monitoring, mechanical ventilation, and/or IV fluids and vasopressors as needed. Monitor other organ function closely. Manage constitutional symptoms and organ toxicities as per institutional practice. Rule out other inflammatory conditions that can mimic CRS (e.g., sepsis). If no improvement within 24 hours, initiate workup and assess for signs and symptoms of HLH or MAS. Administer IV corticosteroids (e.g., methylprednisolone 2 mg/kg/day or dexamethasone 10 mg every 6 hours). Consider anti-cytokine therapy.^e For patients who are refractory to anti-cytokine therapy, experimental treatments^f may be considered at the discretion of the investigator and in consultation with the Medical Monitor. Hospitalize patient until complete resolution of symptoms.

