ASTCT = American Society for Transplantation and Cellular Therapy; BiPAP = bi-level positive airway pressure; CAR = chimeric antigen receptor; CPAP = continuous positive airway pressure; CRS = cytokine-release syndrome; CTCAE = Common Terminology Criteria for Adverse Events; eCRF = electronic Case Report Form; HLH = hemophagocytic lymphohistiocytosis; ICU = intensive care unit; IRR = infusion-related reaction; IV= intravenous; MAS = macrophage activation syndrome; NCCN = National Cancer Comprehensive Network; NCI National Cancer Institute.

Note: These management guidelines have been adapted from the NCCN guidelines for the management of CAR T-cell-related toxicities (Version 2.2019).

^a Grading system for these management guidelines is based on ASTCT consensus grading for CRS. NCI CTCAE (version as specified in the protocol) should be used when reporting severity of IRRs, CRS, or organ toxicities associated with CRS on the Adverse Event eCRF. Organ toxicities associated with CRS should not influence overall CRS grading.

^b Fever is defined as temperature 38C not attributable to any other cause. In patients who develop CRS and who then receive anti-pyretic, anti-cytokine, or corticosteroid therapy, fever is no longer required when subsequently determining event severity (grade). In this case, the grade is driven by the presence of hypotension and/or hypoxia.

^c Symptomatic treatment may include oral or IV antihistamines, anti-pyretics, analgesics, bronchodilators, and/or oxygen. For bronchospasm, urticaria, or dyspnea, additional treatment may be administered as per institutional practice.

^d Low flow is defined as oxygen delivered at 6 L/min, and high flow is defined as oxygen delivered at 6 L/min.

^e Resumption of atezolizumab may be considered in patients who are deriving benefit and have fully recovered from the immune-mediated event. The decision to rechallenge patients with atezolizumab should be based on investigator's assessment of benefit-risk and documented by the investigator (or an appropriate delegate). Medical Monitor is available to advise as needed. For subsequent infusions, administer oral premedication with antihistamines,

anti-pyretics, and/or analgesics, and monitor closely for IRRs and/or CRS. Premedication with corticosteroids and extending the infusion time may also be considered after assessing the benefit-risk ratio.

^f Refer to *Riegler et al. (2019)*.

H) Management Guidelines for Pancreatic Events, Including Pancreatitis

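### Section 7.2.3 bars atezolizumab for good after a Grade 4 or recurrent Grade 3 immune-mediated reaction, but 11 of the 14 to 16 non-endocrine, non-HCC Appendix 1 rows that cover Grade 4 leave a way back to the drug

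*Combined protocol and SAP*

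**What the plan says.** Three parts of the protocol tell a site what to do with atezolizumab after a severe immune-mediated event.

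- **Section 7.2.3** gives the rule: "Atezolizumab must be permanently discontinued for any Grade 3 immune-mediated adverse reaction that recurs and for any Grade 4 immune-mediated adverse reactions". The only exception is endocrine disorders controlled by hormone replacement. The same section refers sites to Appendix 1 for organ-specific management, for example "Management guidelines for hepatic events are provided in Appendix 1". For myocarditis, meningoencephalitis and nephritis it says that patients should be treated as the appendix sets out.
- **Section 7.2.2**, on dose modification, accepts either a temporary or a permanent interruption after a related Grade 3 or 4 event.
- **Appendix 1** works organ by organ. Most severe-grade rows tell the site to "permanently discontinue atezolizumab and contact Medical Monitor", and a footnote to that instruction adds: "Resumption of atezolizumab may be considered in patients who are deriving benefit and have fully recovered from the immune-mediated event". In most parts the footnote leaves the decision to the investigator's documented view of benefit and risk, with the Medical Monitor available for advice. Myocarditis is stricter: "Patients can be re-challenged with atezolizumab only after approval has been documented by both the investigator (or an appropriate delegate) and the Medical Monitor".

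Section 9.4 points elsewhere again, to the atezolizumab Investigator's Brochure, for managing immune-mediated events.

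**The concern.** Section 7.2.3 uses mandatory language and names its own exception. Rechallenge after recovery is not that exception. A site that reads only the relevant Appendix 1 row, as 7.2.3 itself invites it to do, will often find a route back to the drug after an event for which the body text closes it.

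The stake is patient safety and uniform conduct. The study has 15 sites. Two of them facing the same Grade 4 event could act in opposite ways, each citing the protocol, and one would be giving atezolizumab to a patient who should have stopped. That site would also be in breach of 7.2.3 while relying on text that appears to permit what it did.

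**Working it through.** There is no plan figure to reproduce, so the check sets the 7.2.3 rule against each Appendix 1 row that covers Grade 4. Endocrine rows (part D) and the HCC rows in part B are left out. The question for each row is whether the row or its footnote lets atezolizumab be given again.

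| Appendix 1 part | Row | Way back to atezolizumab |
|---|---|---|
| B | Hepatic, Grade 3 or 4 | Footnote c, investigator |
| C | Diarrhea/colitis, Grade 4 | Footnote c, investigator |
| E | "Ocular event, Grade 3 or 4" | Footnote c, investigator |
| F | Myocarditis, Grade 2-4 | Footnote a, dual approval |
| G | CRS/IRR, Grade 4 | Footnote e, investigator |
| H | Amylase/lipase, Grade 3 or 4 | Row text: withhold, then restart at Grade 1 |
| H | Pancreatitis, Grade 4 | Footnote c, investigator |
| I | Dermatologic, Grade 4 | Footnote c, investigator |
| J | Myasthenia gravis/Guillain-Barré, any grade | Footnote c, investigator |
| K | Meningoencephalitis, all grades | Footnote a, investigator |
| M | Myositis, Grade 4 | Footnote c, investigator |
| I | SJS/TEN, any grade | None |
| L | Renal, Grade 3 or 4 | None |
| O | Skin reaction, Grade 4 | None |
| O | SJS/TEN, no grade in the row (7.2.3 item 15: any grade) | None |
| N | Suspected HLH/MAS, ungraded | None |

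**Numerator.** Investigator footnote 9 + dual approval 1 + direct restart 1 = 11.

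**Denominator.** Rows whose own label names Grade 4, any grade or all grades: 11 + 3 = 14. Adding the part O SJS/TEN row gives 15, and adding HLH/MAS gives 16. The numerator is 11 throughout.

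**Sensitivity.**
- The pulmonary stop row is printed as Grade 3 only, although the Grade 2 row above it speaks of Grade 3 or 4. Read that way, the labelled count becomes 12 of 15.
- The CRS/IRR row is defined clinically ("with hypotension requiring multiple vasopressors (excluding vasopressin) and/or hypoxia requiring oxygen by positive pressure"), and its footnote says "Grading system for these management guidelines is based on ASTCT consensus grading for CRS", whereas the trial otherwise grades by CTCAE. Table 3 in section 9.4 lists CRS and infusion reactions as immune-related. If the row is nevertheless dropped, the count is 10 of 13 to 15.
- If amylase/lipase is dropped as well, it is 9 of 12 to 14.

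**Recurrent Grade 3.** Three instructions lead to a stop that carries the resumption footnote: recurrent amylase/lipase elevation, recurrent Grade 2 or 3 pancreatitis, and recurrent Grade 3 myositis (handled as Grade 4). The Grade 3 colitis and dermatologic rows are silent on recurrence. They are not counted, because 7.2.3 fills that gap.

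**Kind of conflict.** In ten rows the footnote is a permission, so a site that never resumes satisfies both texts. The amylase/lipase row is an instruction. Section 9.4.1 lists a lipase increase among immune-related events. For a Grade 4 rise judged immune-mediated that settles to Grade 1, the row and 7.2.3 cannot both be followed.

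**The case against.** The strongest reply is that the footnote is a deliberate, specific exception to a general rule. It applies only to recovered patients who are benefiting, it requires documentation, and the stop itself triggers contact with the Medical Monitor. Section 8.2 also requires immediate safety concerns to be discussed with the Sponsor. Section 7.2.2 leaves room for a temporary interruption, and for myocarditis and meningoencephalitis 7.2.3 itself hands treatment to Appendix 1.

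Much of this stands. It shows that rechallenge may be intended and that it would not be unsupervised. It does not reconcile the texts: none of these safeguards says that the mandatory stop can be lifted, and no sentence found gives either source precedence. The appendix is also uneven. Myocarditis needs two documented approvals, while meningoencephalitis and Guillain-Barré need only the investigator's assessment. Grade 4 skin events carry the footnote in part I but not in part O.

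A second reply is that superscripts read from a PDF are fragile. Part M defines a footnote that no row cites, and the renal row may have lost its marker. A lost marker there would raise the count. Parts F and K do not depend on marker reading, since each has one row and one footnote.

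A reader might infer that all eleven rows contradict 7.2.3 outright. They do not: ten are permissive, and the one direct conflict depends on the rise being immune-mediated.

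**Conclusion.** The inconsistency is real and should be fixed. Eleven of the 14 to 16 non-endocrine, non-HCC rows that cover Grade 4 do not enforce 7.2.3. Ten permit resumption by footnote, and one directs it. Three recurrence instructions share the weakness.

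The count assumes that the printed footnote markers are right, that CRS/IRR falls under 7.2.3 despite its different grading scale, and that an amylase or lipase rise can be immune-mediated. The documents give no frequency for these events, so the number of patients affected cannot be estimated.

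Two further inferences are not supported. Nothing shows an effect on the objective response rate or on the Simon stopping rule. Nor do the documents establish that 7.2.3 is the text that ought to prevail, which is a clinical choice for the sponsor. The different hold limits (42 days past the due dose in 7.2.2, 12 weeks from onset in Appendix 1) are a minor matter, because a site can meet both by obtaining the Coordinating Investigator approval that 7.2.2 describes.

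**What to change.** State one governing rule in 7.2.2, 7.2.3 and Appendix 1, by one of two routes.

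**(a) Section 7.2.3 governs.** State that the resumption footnotes do not apply after a Grade 4 or recurrent Grade 3 immune-mediated event.
- In the five rows confined to Grade 4 (colitis, CRS/IRR, pancreatitis, dermatologic, myositis), delete the footnote marker.
- In the five mixed-grade rows that carry a footnote (hepatic, ocular, myocarditis, myasthenia gravis/Guillain-Barré, meningoencephalitis), add the limit and leave first Grade 3 events as they are.
- Split the amylase/lipase row so that an immune-mediated Grade 4 rise is a permanent stop.
- Apply the limit to recurrent Grade 3 in the three recurrence instructions.
- In 7.2.2, say that 7.2.3 decides when an interruption must be permanent.

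**(b) Rechallenge is intended.** Write it into 7.2.3 as an explicit exception, preferably requiring in every affected row the documented approval by investigator and Medical Monitor that myocarditis already has. Align 7.2.2 and the amylase/lipase row with it.

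Either route is a text-only amendment with a notice to sites. Route (a) takes rechallenge away from some recovered patients who are benefiting. Route (b) keeps it but adds an approval step.
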